10.5.3 Timing

The single blinded interim analysis is planned once 360 (360-10 color balance masses=350) completed image sets are read by each reader and the data become available. The interim analysis will be performed by an independent, unblinded third party statistician who will make recommendations below to Seno Medical Inc. based on the results from this initial cohort of masses:

1. Sample Size Calculation:

___ One additional block is required (480 masses) OR

___ Two additional blocks are required (600 masses) OR

___ Three additional blocks are required (720 masses) OR

___ Four additional blocks are required (840 masses) OR

___ Four additional blocks (840 masses) are not sufficient but reads should continue because there is a reasonable chance to reach statistical significance based on the conditional power assuming the alternative hypothesis holds.

___ *Four additional blocks (840 masses) are not sufficient, reads should not continue because there is not a reasonable chance to reach statistical significance based on the conditional power assuming the alternative hypothesis holds.*

To maintain blinding to the interim results, no specific results from the interim analysis will be shared by the unblinded party performing the analysis with Seno or any other study participant, and only one of the above recommendations will be provided. Seno retains the right to accept, not accept, or modify any recommendation concerning changes to conduct of the study.

There are no plans to stop the study early for benefit or a positive outcome on the basis of the interim analysis results. No alpha will be spent to perform this interim analysis since this analysis is for sample size re-estimation only (1). Under no circumstances will the alternative hypothesis be modified as a result of this analysis. The final analysis will include the results from the n=360 (360-10 color balance masses=350) interim analysis.

10.5.4 Execution

The unblinded biostatistician will only evaluate the overall SD which was the nuisance parameter driving sample size for the fixed 10% difference to be detected. The unblinded biostatistician will not need to take the observed delta into account. Other than the preplanned sample size calculation to determine the remaining blocks required to complete the study, no

other information will be revealed to the Sponsor or to any other members of the analysis team. The IA will be executed to the blinded principle.

10.6 Protocol Deviations

The protocol deviations will be reviewed in advance of the interim and final analyses for any unreadable, unevaluable, or skipped image sets. A Protocol Deviation Meeting will be held among results-blinded parties prior to the preplanned n=360 interim analysis and final analysis to address how to handle impacted image sets.

At study completion, the number and type of protocol deviations will be presented overall and by reader to determine whether there are statistical concerns. The biostatistician will report findings to the study sponsor.

10.7 Outcomes

Outcomes will be analyzed according to the PIONEER Truth Panel findings and the pathology diagnosis (if available) as truth; Truth Panel Benign (TPB) will be a benign diagnosis. The final analyses will be performed following database lock.

10.8 Hierarchical Testing

To extend labeling claims beyond the primary endpoint, a hierarchical testing strategy will be used to control Type 1 error associated with testing the primary endpoint and three secondary endpoints in the following pre-defined order until statistical significance is no longer reached in support of extended labeling:

- Increase in specificity for fixed 98% sensitivity.
- NLR
- PLR
- pAUC over 95% to 100% sensitivity

No other endpoints are to be included as labeling claims.

10.9 Data Analyses

All analyses will be performed in a GCP-controlled environment using the Hillis software (see references 3-7), SAS v9.3 or higher, and StatXact v10 or later unless otherwise specified.

See the companion SAP for further details.

All significance testing will be two-sided; results will be presented using two-sided p-values and two-sided 95% confidence intervals.

All final analyses will exclude the 29 Color Balanced masses; 350 masses will be analyzed at the interim analysis timepoint. This excludes the 10 Color Balance masses. For the final analysis, the 29 Color Balanced masses will be replaced from the overage and the PIONEER Pilot Study if there are insufficient masses among the overage masses.

Methods of analysis will be based on MRMC analysis methods by Obuchowski and Rockette where both reader and mass are random effects (see references 7-13). Two-sided 95% confidence intervals will be computed for the individual outcomes (IUS, Imagio (IUS+OA)) and paired differences.

The same approach will be used to compute the differences in partial ROC AUC and full ROC

AUC, sensitivities, specificities, and paired differences, for benign and malignant masses. These analyses will be performed for IUS versus Imagio (IUS+OA) SG).

For each endpoint, subgroup analyses will be performed in the same manner for those with a prior mammogram as well as for those without a prior mammogram.

1. Sensitivity, Specificity, Partial ROC AUC, Full ROC AUC, and Specificity for Fixed Sensitivity

Individual reader specificity and sensitivity will be calculated from simple counts for the 2% POMs to construct the respective ROC curves for IUS, the Imagio (IUS+OA).

For sensitivity and specificity, GEE and ANOVA will be used to compute differences as well as to compute the two-sided 95% confidence intervals for the OA-IUS differences.

The specificity advantage for fixed 98% sensitivity will be the primary endpoint; a 10% absolute advantage for Imagio vs IUS in specificity for fixed 98% sensitivity is considered to be clinically relevant; this drives the final sample size calculation. The Hillis software will be used to analyze the primary endpoint as well as for the partial and full ROC AUCs. The AUCs will be computed from the respective ROC curves which are generated according to the POMs.

Specificity and sensitivity are calculated using this fixed 2% cutoff. Please be assured that the OR-DBM MRMC 2.51 (Hillis) software does not pick or use a fixed cutoff. In our application, the Hillis software computes AUC, partial AUC, specificity gain at fixed sensitivity, and sensitivity gain at fixed specificity using a full factorial ANOVA incorporating terms for readers, masses, and modalities. The gain in specificity can be computed at a wide range of sensitivities. The 98% sensitivity corresponds to a 2% false negative (FN) rate, but this unrelated to the use of a fixed 2% POM cutoff for clinical decision making.

The partial AUC will be computed over the 95-100% sensitivity range using PROPROC. To compute the specificity advantage for fixed sensitivity, interpolation may be required; a fixed sensitivity will be targeted, e.g., 98%. To compute the specificity advantage and the partial area under the ROC, the specificities and sensitivities may need to be further computed from the ROC curves as needed. The variances will be computed to construct the two-sided 95% CIs for Imagio (IUS+OA), IUS, and for the respective pairwise Imagio (IUS+OA) - IUS difference.

2. NLR and PLR

NLR and PLR will be analyzed using the logarithmic transformation and the delta method. Calculations will be performed using MATLAB script: DLRATIOS.M. The method of Nofuentes (14) will be used; this reflects that the NLR and PLR are both ratios of independent random variables. The DLRATIOS routine computes the standard deviation for the ratios of two independent random variables corresponding to the sensitivity and specificity which are both used to compute NLR and DLR.

[figure not shown]

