10. STATISTICAL CONSIDERATIONS

10.1 General Design Issues

BBRF will implement the Reader-02 Pivotal Study Mass Sampling Plan to randomly select masses.

The unit of measurement for reader-based outcomes is at the reader-mass level. The Reader-01 Feasibility Study demonstrated that readers could conduct POM evaluation separately for IUS and then for Imagio (IUS+OA) (primary) to evaluate the primary and secondary effectiveness endpoints.

The primary endpoint is to show a specificity advantage for fixed 98% sensitivity (OR-DBM); this diffuses the tradeoff between FNs and FPs if the FN rate is the same. The sensitivities and specificities will be calculated overall and per reader using generalized estimating equations (GEE) and the analysis of variance (ANOVA) modeling as well as for observed without adjustment.

For each primary and secondary endpoint, Imagio (IUS +OA) data will be compared to IUS data, with the analysis stratified by the availability/non-availability of mammogram images.

The specificity advantages will be computed for fixed sensitivity (e.g., 98% target) with interpolation used by calculating the specificities and sensitivities from the estimated ROC

curve as needed. This same principle will be used to construct the partial ROC curves and to compute the area under the ROC curve over 95-100% sensitivity. Specificity at fixed sensitivity and partial AUC will be determined from parametric ROC curves constructed using techniques such as binormal or PROPROC models.

The supporting statistical methodology (2-8) relies on publications by Hillis, Rockette, Obuchowski, and Metz in accordance with best regulatory statistics practice. Readers will be treated as correlated and as random effects.

The Reader-01 Feasibility Study results were used to determine the Reader-02 Pivotal Study sample size. The overall difference in specificity for fixed 98% sensitivity will be assessed to judge if the Reader-02 Pivotal Study can be conducted with 80% power to detect a 10% absolute advantage in specificity (alternative hypothesis) versus no absolute advantage (null hypothesis) with two-sided 5% Type I error where both readers and masses (image sets) are considered to be random effects; this approach leads to the most conservative test given that it is based on the largest source of inter-reader variability. Reader-01 Feasibility Study data will not be used or combined with any subsequent Reader-02 Pivotal Study data.

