10.2 Reader / Image Set Sample Size

The sample size will be based on the primary effectiveness endpoint, namely the gain in specificity for fixed 98% sensitivity. This calculation depends upon the number of image sets (one per mass) to be read, the number of readers, as well as the inter-reader variability associated with the underlying models used for analysis.

The test of the primary hypothesis is powered to detect a 10% absolute specificity advantage (superiority) as the alternative hypothesis with no specificity advantage as the null hypothesis. The primary endpoint will be evaluated in the following testable hypotheses:

$$H_0: S_{\text{Imagio}} = S_{\text{IUS}}$$

$$H_1: S_{\text{Imagio}} \neq S_{\text{IUS}}$$

where S_{Imagio} and S_{IUS} represent specificity, values associated with Imagio (IUS + OA) and IUS.

The sample size calculations conservatively assume that both readers and masses are random effects; an ANOVA model will be used to compute sample size. The sample size was computed using the following statistical software written by Stephen Hillis and entitled: Multi-Reader Sample Size Program for Diagnostic Studies [<http://perception.radiology.uiowa.edu>].

For 80% power, a two-sided hypothesis test with a two-sided 5% alpha, and 15 readers, a sample size of 854 image sets is needed to detect a 10% absolute advantage in specificity for Imagio (IUS + OA) vs IUS, assuming a fixed 98% sensitivity and the same intra- and inter-reader standard deviation observed in the Reader-1 Feasibility Study.

The supporting calculations including the software output follow:

Results for Feasibility variance estimates

User-supplied parameter or pilot-study values:

Design : factorial
Tests : nonequivalence
Readers and cases : both readers and cases random
Input values : treat as known
Alpha : 0.05
Input Format : OR variance components with error covariances
test*reader var comp : 0.00203538
Error variance : 0.03571
Cov1 : 0.01106919
Cov2 : 0.0061484
Cov3 : 0.0043063
c* : 120

User-supplied desired power, proposed readers & cases values

Desired Power : 0.8
Proposed max readers : 15
Proposed max cases : 2000
Proposed min readers : 15
Proposed min cases : 20

Corresponding OR variance components, covariances, and correlations

test*reader var comp : 0.00203538
Error variance : 0.03571
Cov1 : 0.01106919
Cov2 : 0.0061484
Cov3 : 0.0043063
r1 : 0.309974517
r2 : 0.172175861
r3 : 0.120590871

Sample Size Results

effect size :	readers :	Cases :	POWER

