10.3 Additional Hypothesis Tests

The following two-sided hypothesis tests will be applied using the observed estimates for NLR and PLR as well as using the PROPROC for the partial ROC AUC:

- NLR:
 - $H_0: NLR_{IUS} = NLR_{Imagio}$ vs
 - $H_A: NLR_{IUS} \neq NLR_{Imagio}$ representing a reduction
- PLR:
 - $H_0: PLR_{IUS} = PLR_{Imagio}$ vs
 - $H_A: PLR_{IUS} \neq PLR_{Imagio}$ representing an increase
- Partial ROC AUC:
 - $H_0: pAUC_{IUS} = pAUC_{Imagio}$ vs
 - $H_A: pAUC_{IUS} \neq pAUC_{Imagio}$ representing an increase

Hierarchical testing will be applied to seek labeling claims if warranted by the pre-defined testing procedure (see Section 10.8).

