2.1.8. Effectiveness Methodology

The following approaches (Hillis OR-DBM MRMC 2.51) were used to treat readers as correlated and as random effects in analyses. [REDACTED]

[REDACTED]

[REDACTED]

Analysis 1 treats both as random, and thus results generalize to both the population of readers and cases – this is the situation for which the DBM and Obuchowski-Rockette (OR) procedures were originally designed. However, within the OR/DBM analysis framework one can also analyze the

data treating only cases as random (Analysis 2) or readers as random (Analysis 3), although we note that these analyses are not unique to OR/DBM. Analyses 2 and 3 are viewed as supportive analyses while Analysis 1 is viewed as the primary analysis approach.

For all three analyses, the null hypothesis of equal treatments is tested in part (a), diagnostic test difference 95% confidence intervals are given in part (b), and individual diagnostic test two-sided 95% confidence intervals are given in part (c) of the output. For the DBM procedure, parts (a) and (b) are based on the diagnostic test x reader x mass ANOVA of jackknife pseudo-values while part (c) is based on the reader x case ANOVA of jackknife pseudo-values for the specified diagnostic test. For the OR procedure, parts (a) and (b) are based on the diagnostic test x reader ANOVA of reader-performance outcomes (e.g., AUCs) while part (c) is based on the reader ANOVA of reader-performance outcomes for the specified diagnostic test. [REDACTED]

Different denominator “error terms” (these are the denominators used for the F statistics) are used as indicated for parts (a), (b), and (c) according to whether reader and case are treated as fixed or random factors, and their formulas are provided in the output. Note that the diagnostic test confidence intervals in part (c) are based only on the data for the specified diagnostic test, rather than the pooled data. Diagnostic test difference 95% confidence intervals for each reader are presented in part (d) of Analysis 2: for DBM each interval is based on the diagnostic test x mass ANOVA table for the specified reader; for OR each interval is based on the OR variance and Cov1 estimates computed separately for each reader.

Analysis 1

Our planned analysis (Analysis 1) treats both readers and masses as random samples. Results apply to the reader and mass populations — this is the situation for which DBM and OR were initially created.

Analysis 2

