2.1.9. Effectiveness Analysis

There is a formal test of hypotheses for the primary endpoint. Other p-values that are generated for other endpoints will be regarded as descriptive statistics. Imagio (IUS+OA) represents the reader input after viewing the Imagio (IUS+OA) images and SenoGram results. IUS represents the reader input prior to any IUS feature scoring, but after reader training on Imagio (IUS+OA).

The following will be used to assess the pivotal study.

Table 1: Effectiveness Analysis for Study Endpoints

Endpoints by Cohort	Analysis/Software
Primary	
Gain in specificity Imagio (IUS+OA) vs. IUS at fixed 98% sensitivity interpolated from the ROC AUC curves using methods of Obuchowski-Rockette (OR). Effect estimates (two-sided 95% CIs) will be derived using OR-DBM MRMC methods. The interim analysis to re-assess pivotal study sample size will be determined using OR-DBM MRMC sample size program.	OR-DBM MRMC Sample Size: OR-DBM-MRMC Power program, nQuery v7, SAS (PROC POWER), and/or PASS v15.0.5.

Secondary	

Partial AUC: Difference (Imagio (IUS+OA) vs. IUS) in partial Receiver Operator Characteristic (ROC) Area Under the Curve (AUC) for 95-100% sensitivities using the OR methods.
	
OR-DBM

Specificity and Sensitivity: Specificity is defined using the percent with a negative result (POM <2%) among all benign+TPB masses (to include all high-risk masses). Sensitivity is defined using the percent with a positive result (POM >2%) among all malignant masses.
 
Observed and model-adjusted specificity and sensitivity will be reported for Imagio (IUS+OA) vs. IUS using a 2% Probability of Malignancy (POM) cutoff.
 
These analyses will be repeated for POM cutoffs of 1%, 3%, 4%, 5%, 6%, and 7%.
 
High risk masses will be included in the calculations for specificity.
	
SAS PROC GEE and MIXED treating masses as independent observations and readers as correlated and then readers as independent and masses as correlated.
 
Two-sided 95% confidence intervals (CIs) for sensitivity and specificity will be computed for IUS, for Imagio (IUS+OA), and for the pairwise difference.
 
Confidence intervals will be constructed treating masses as independent observations with readers as correlated and then readers as independent with masses correlated.

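### NLR and PLR, steps 2 and 3 of the labeling hierarchy, have a delta-method variance with no stated reader component, and the both-random rule is not carried to them

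*Combined protocol and SAP*

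**What the plan says.** **Status of the tests.** Protocol 10.8 says that "a hierarchical testing strategy will be used to control Type 1 error associated with testing the primary endpoint and three secondary endpoints", in the order primary, NLR, PLR, pAUC. Protocol 10.3 adds: "The following two-sided hypothesis tests will be applied using the observed estimates for NLR and PLR". SAP 2.1.11 and 2.1.11.4 agree that these are formal tests. The opening of SAP 2.1.9 does not: there only the primary endpoint has a formal test, and all other p-values are descriptive.

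**Variance method.** Protocol 10.9, item 2, uses the log transformation, the delta method and a MATLAB routine, following reference 14. By its title, that paper compares the likelihood ratios of two binary tests in paired designs. The routine is described thus: "The DLRATIOS routine computes the standard deviation for the ratios of two independent random variables corresponding to the sensitivity and specificity". The NLR and PLR row of SAP Table 1 repeats the log and delta method for a univariate interval.

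**General reader rule.** Protocol 10.1: "Readers will be treated as correlated and as random effects". Protocol 10.9 bases its methods on Obuchowski-Rockette analysis "where both reader and mass are random effects (see references 7-13"), and extends that approach by name to partial and full AUC, sensitivities, specificities and paired differences. SAP 2.1.8 says its OR-DBM approaches "were used to treat readers as correlated and as random effects in analyses".

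**Sensitivity and specificity in the SAP.** Table 1 assigns them GEE and mixed models "treating masses as independent observations and readers as correlated and then readers as independent and masses as correlated".

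**The concern.** Every mass is read by 15 readers under both modalities. The uncertainty of an overall NLR or PLR difference therefore includes reader-by-modality variation and the correlation among different readers' reads of the same mass. A routine for one pair of binary tests does not obviously contain either, and its description mentions neither.

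The stake is a label claim. If no modality difference exists anywhere, the primary test stands in front and limits the error. The exposure arises when the primary effect is real. NLR could then be claimed when it is not better, or PLR could be claimed when NLR truly improves and PLR does not. NLR and PLR also gate pAUC. In addition, if the input to the routine is not fixed beforehand, the p-value depends on a choice that could be made after the data are seen.

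**Working it through.** **1. Does the readable text carry the reader rule to NLR and PLR?**

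- Protocol 10.9 ties the both-random rule to references 7-13. Item 2 cites reference 14.
- The list of measures under the both-random approach includes sensitivities and specificities. It does not include NLR or PLR.
- The OR-DBM software, which has terms for readers, masses and modalities, is assigned to the primary endpoint and the AUCs. It is not assigned to the likelihood ratios.
- Protocol 10.3 and SAP 2.1.10 base the NLR and PLR tests on observed estimates. Neither says how 15 readers' results are combined.

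So no reader component is stated, and neither is any link from the both-random variances to the routine.

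**2. Inputs for the size.** The documents give no variance components for NLR or PLR. As a stand-in I use the feasibility components for the primary endpoint in Protocol 10.2: "test*reader var comp : 0.00203538", error variance V = 0.03571, Cov1 = 0.01106919, Cov2 = 0.0061484, Cov3 = 0.0043063, c* = 120, r = 15 readers, effect 0.10, two-sided alpha 0.05.

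**3. Reproduce the plan's figure.** With TR the test-by-reader variance:

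- D = TR + (120/c)[V − Cov1 + (r−1)(Cov2 − Cov3)]
- M = TR + (120/c)[V − Cov1 − (Cov2 − Cov3)]
- Noncentral F with λ = r × 0.10²/(2D), df1 = 1, df2 = (r−1)D²/M²

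Here V − Cov1 = 0.02464081 and 14 × (Cov2 − Cov3) = 14 × 0.0018421 = 0.0257894, which sum to 0.0504302. At c = 854, D = 0.00203538 + 0.140515 × 0.0504302 = 0.0091216, λ = 8.22, df2 = 42.4 and power is 0.8001, against 0.801 stated. The smallest c that reaches 0.80 is 854, as the plan says. At 840 power is 0.795, matching the SAP's 79%.

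**4. Split the variance at 840 masses.** 120/840 = 0.142857.

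- Test-by-reader: 0.0020354, 22% of D
- Between-reader covariance: 0.142857 × 0.0257894 = 0.0036842, 40% of D
- Remainder: 0.142857 × 0.0246408 = 0.0035201, 38% of D
- D = 0.0092397

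**5. Drop the reader terms.** The variance of the modality difference is 2D/r. If only a share s of it is used, a nominal two-sided 5% test has true error of about 2[1 − Φ(1.96√s)] under a normal approximation.

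| Masses | Variance used | SE of difference | s | True error |
|---|---|---|---|---|
| 840 | all terms | 0.0351 | 1.00 | 5% |
| 840 | no test-by-reader | 0.0310 | 0.780 | 8.4% |
| 840 | also reads independent between readers | 0.0217 | 0.381 | 22.6% |
| 480 | all terms | 0.0442 | 1.00 | 5% |
| 480 | no test-by-reader | 0.0410 | 0.861 | 6.9% |
| 480 | also reads independent between readers | 0.0287 | 0.421 | 20.4% |

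The third and sixth rows still keep the pairing of the two modalities within a reader, through V − Cov1.

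**The case against.** The best reply is that the plan already covers this. Its general rule makes readers random, and Protocol 10.9 places sensitivities and specificities, the two ingredients of NLR and PLR, under the both-random approach by name. A delta method passes on whatever variances it is given, so the routine could be fed both-random ones. The routine itself is not in the documents, and reference 14 can be judged only by its title.

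Much of this stands. A reader might infer that the routine certainly ignores readers, or that all 15 readers' reads will be pooled as if independent. The documents say neither. A reader might also infer from SAP Table 1 that no both-random model for sensitivity and specificity exists in the plan. Protocol 10.9 contradicts that, so the two texts need reconciling.

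The reply does not close the gap, because no sentence connects the both-random variances to the NLR and PLR tests. Even if they were connected, treating sensitivity and specificity as independent would remain a problem overall. For a single reader independence is reasonable, since malignant and benign masses are disjoint sets. Across random readers, differences in threshold or accuracy make the two correlated, so their joint covariance is needed.

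Two further limits are fair. The components in Protocol 10.2 belong to specificity at 98% sensitivity, whereas NLR and PLR use observed rates at a POM cutoff. Also, parts of SAP 2.1.8, Table 1 and 2.1.11 are redacted, and the PIONEER table cited in Table 1 is not available. The point therefore rests on Protocol 10.9, which is readable.

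**Conclusion.** The point holds as a gap in specification with material consequences. Two formal label-claim tests have a variance method whose readable description names only sensitivity and specificity, and the both-random rule is not extended to them. If the method is applied to the 15-reader data without reader terms, the overall standard errors will generally be too small.

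The size is illustrative: about 8% for a nominal 5% test at 840 masses (7% at 480) without test-by-reader variance, and about 23% (20%) if reads are also treated as independent between readers. This assumes that the primary endpoint's components resemble those of the log ratios, and it uses a normal approximation. A reader might take these as false-claim rates. They are not: they are two-sided error rates for one test in isolation, before the primary gate and without regard to direction. The documents do not support a figure for the gated claim rate.

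The primary endpoint and pAUC are not affected, because both are assigned to OR-DBM MRMC. Separately, SAP 2.1.9 contradicts the hierarchy on whether secondary p-values are formal or descriptive.

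**What to change.** - For the overall NLR and PLR tests, specify a variance with readers and masses both random. Options are Obuchowski-Rockette analysis of reader-level log ratios, with a rule set in advance for a reader with no false negatives; a delta method fed by the joint both-random covariance of sensitivity and specificity; or a bootstrap that resamples readers and masses. Name one.
- Keep the MATLAB routine for per-reader results.
- Reconcile the two one-way-clustered fits for sensitivity and specificity in SAP Table 1 with the both-random approach in Protocol 10.9.
- Correct the SAP 2.1.9 sentence on descriptive p-values so that it agrees with Protocol 10.8 and SAP 2.1.11 and 2.1.11.4.

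The cost is SAP wording and some programming, probably wider intervals, and some loss of power for NLR and PLR. No new reads are needed.
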